7. PLANNED ANALYSIS

For End-Of-Text (EoT) tables, the set of summary statistics is: N / Mean / standard deviation (SD) / standard error (SE) / Min / lower quartile (Q1) / Median / upper quartile (Q3) / Max. The 1st and 99th percentiles might be substituting minimum and maximum in tables with open-ended values to safeguard against implausible extremes. Final decision will be made at the final BRPM.

Geometric means and gCV will be added to the presentation or replace the presentation of mean, standard error and standard deviation for parameters (e.g. NT-proBNP) that follow a log-normal distribution rather than a normal distribution.

Statistical parameters will be displayed to a defined number of decimal places as specified in the BI guideline “Standards for Reporting of Clinical Trials and Project Summaries” [\(3\)](#)

Tabulations of frequencies for categorical data will include all possible categories and will display the number of observations in a category as well as the percentage (%) relative to the respective treatment group (unless otherwise specified, all patients in the respective patient set whether they have non-missing values or not). Percentages will be rounded to one decimal place. The category missing will be displayed only if there are actually missing values.

Disposition of the patient population participating in the trial will be analysed by treatment groups and presented in the clinical trial report as a frequency distribution. The number of patients participating (screened, randomised, screened but not randomised, etc.) in the study by region, country and, for treated patients, centre, will also be analysed by treatment group and presented as a frequency distribution.

Disposition as required for reporting for the trial in EudraCT will be provided. Enrolment will be summarised by country and by age group for reporting in EudraCT.

The reasons for not randomising screened patients will be summarised descriptively.

The frequency of patients with iPDs will be presented by treatment group for the randomised set. The frequency of patients in different analysis sets will also be analysed for each treatment group.

7.1 DEMOGRAPHIC AND OTHER BASELINE CHARACTERISTICS

Only descriptive statistics are planned for this section of the report.

Demographics and baseline characteristics will be analysed based on RS. Demographics will be repeated on the TS if the number of patients in the analysis sets differ by more than 5%. Standard descriptive analysis and summary tables will be presented. These summary tables will include description of variables detailed in [Section 6.4](#). In addition, descriptive analyses of the following continuous variables measured at baseline will be presented: Age, body mass index (BMI), time since HF-diagnosis, systolic blood pressure (SBP), diastolic blood pressure

(DBP), weight, eGFR, NT-proBNP, heart rate. For patients with diabetes at baseline, HbA_{1c} at baseline will be shown descriptively.

7.2 CONCOMITANT DISEASES AND MEDICATION

Only descriptive statistics are planned for this section of the report using the randomised set. Concomitant medication use will be summarised by Anatomical-Therapeutic-Chemical classification level 3 (ATC1-ATC2-ATC3) and preferred name. Summaries will be presented for concomitant therapies taken at baseline and separately those added after baseline.

Separate summaries of use of heart failure-related drugs (e.g. ARNi, beta-blockers, ivabradine, diuretics, ACE-inhibitors, ARBs, MRAs, cardiac glycosides), anticoagulants, acetylsalicylic acid (ASA), or lipid lowering drugs at baseline and separately those for added after baseline will be presented. Definitions of these medication groups are based on World Health Organization Drug Dictionary (WHO DD) and are stored in the Project Data Management and Analysis Plan (PDMAP).

Use of devices at baseline will also be summarised.

Concomitant diseases will be summarised by system organ class and preferred term. Relevant medical history by treatment group will also be presented. Both summaries will be presented using the randomised set.

The number and percentage of patients receiving the best tolerated treatment for HF symptoms and other common concomitant diseases or symptoms (e.g. hypertension, diabetes, cardiac arrhythmia, fluid retention) according to prevailing guidelines in the opinion of the investigator will be reported.

7.3 TREATMENT COMPLIANCE

Only descriptive statistics are planned for this section of the report. The number and percentage of patients with overall study medication compliance will be reported.

7.4 PRIMARY ENDPOINT

7.4.1 Primary analysis of the primary endpoint

The primary endpoint ‘change from baseline to week 12 in exercise capacity’ as measured by the change from baseline to week 12 in distance walked in 6 minutes will be evaluated using a normal approximation of the Wilcoxon rank test using the randomised set.

For estimation of effect, non-parametric Hodges-Lehmann estimate for the median difference will be used. Corresponding 95% confidence intervals will be displayed. Any confirmatory conclusion such as for hierarchical testing will be based on the result of the Wilcoxon rank test and will not consider the Hodges-Lehmann estimate or the corresponding confidence interval, which are given to support interpretation.

If no 6MWT is available at week 12, an imputed value as defined in Section 7.5 of the CTP will be used.

The primary analysis will be conducted on all randomised patients, regardless of whether on or off-treatment on the day of 6MWT assessment. Where more than one measurement is available for the same day (duplicate measurements), the longest distance walked will be used for analysis. In case more than one 6MWT results in the same distance walked, the first assessment will be used for analysis.

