7.7.1 Power estimation for key secondary endpoints

KCCQ

For power estimation of the KCCQ TSS a treatment difference of 5 points is assumed. In patients with heart failure previous studies have reported a standard deviation of the KCCQ TSS between 13 in the CONFIRM-HF trial and 19-21 in the FAIR-HF trial [[R17-1226](#), [R17-3097](#)].

Using a normal distribution to calculate the probability that an observation X in Empagliflozin group will be less than an observation Y in the control group under the alternative, a sample size of 150 per treatment group will result in approximately 55% to 90% power to detect a 5 point difference between treatment groups at an alpha-level of 5% using a Wilcoxon test, if all questionnaires are available at the end of the trial (see [table 7.7.1: 1](#)).

Due to the Hochberg procedure, if CHQ dyspnea is not significant, an alpha-level of 2.5% will become applicable. [Table 7.7.1:1](#) therefore additionally shows an alpha-level of 2.5 %.

Table 7.7.1: 1 Power Estimation for KCCQ TSS

SD	P(X<Y)	Power for $\alpha = 5\%$	Power for $\alpha = 2.5\%$
13	0.393	89%	83%
15	0.407	79%	71%
17	0.418	69%	59%
20	0.430	55%	44%

While every effort will be made to collect the questionnaire for randomized patients regardless of being on or off treatment, about 5% missing questionnaires may be assumed and are considered for power evaluation in analogy with the primary endpoint.

Results of a simulation of the power with 100000 iterations to detect a 5 point difference between treatment groups in a Wilcoxon test with imputation rules analogously to the primary endpoint, assuming 5% missing questionnaires at week 12 in each treatment arm, a normal distribution for non-missing scores, and alpha of 5% is summarized in the [table 7.7.1:2](#) below.

Table 7.7.1: 2 Simulation of Imputation Rules for KCCQ TSS

SD	Power for $\alpha = 5\%$	Power for $\alpha = 2.5\%$
13	85%	76%
15	73%	61%
17	61%	49%
20	47%	35%

Overall power is reasonable to evaluate superiority of empagliflozin versus placebo assuming a treatment effect of 5 points and a standard deviation that does not exceed 15 points.

CHQ

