7.4.2 Sensitivity analysis of the primary endpoint

Sensitivity analysis for the primary endpoint will include;

- a mixed model repeated measure analysis (MMRM) without imputation of missing values (OC-AD).
- an MMRM restricted to on-treatment values (OC-OT).

The model will include visit-by-treatment interaction and baseline-by-visit interaction. An unstructured covariance structure will be used to model the within-patient errors. Descriptive statistics will be calculated for the value at visit and change from baseline based on OC-AD on the randomised set and based on OC-OT on the treated set. The MMRM analyses will also be shown graphically.

The primary analysis will be repeated restricted to patient in the sensitivity analysis set SensRS1, SensRS2 and SensRS3.

If the mean difference between the treatment groups in 6MWT is above 15m at baseline, the primary analysis will be repeated, but using the ranks of the residuals from the following linear regression model

$$6MWT_{12weeks} \sim 6MWT_{Baseline}$$

with patients without week 12 data ranked below any patient with week 12 assessment similar to the rules for primary analysis.

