7.5 SECONDARY ENDPOINTS

7.5.1 Key secondary endpoints

If the null hypothesis for the primary analysis of the primary endpoint is rejected, and the result is more favourable for empagliflozin, superiority is concluded in the primary endpoint, and the overall type I error is preserved for the test in the next step. In the next step a Hochberg procedure will be applied to account for multiplicity of testing of the key secondary endpoints:

If the largest p-value of the primary analysis of the two key secondary endpoints is below 5%, both null hypotheses of the key secondary endpoints will be rejected. Otherwise, if the smaller p-value of the primary analysis of the two key secondary endpoints is below 2.5%, only the corresponding null hypothesis can be rejected.

If the primary hypothesis of the primary endpoint is not rejected, the tests of the key secondary endpoints are conducted in an exploratory manner.

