7.5.1.1 Primary analysis of the key secondary endpoints

The two key secondary endpoints ‘Change from baseline to week 12 in KCCQ-TSS’ and ‘Change from baseline to week 12 in CHQ-SAS dyspnea score’ are part of the testing strategy.

Both key secondary endpoints ‘Change from baseline to week 12 in heart failure symptoms as measured by the KCCQ TSS’ and ‘Change from baseline to week 12 in CHQ-SAS dyspnea score’ will be evaluated using a normal approximation of the Wilcoxon rank test using the randomised set. For estimation of effect the non-parametric Hodges-Lehmann estimate for the median difference will be calculated.

Change from baseline in both scores will be defined as the endpoint value at week 12 minus the last available endpoint value before start of randomised trial medication.

If no questionnaire is available at week 12, an imputed value as defined in [Section 6.6](#) will be used.

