7.5.1.2 Sensitivity analysis of the key secondary endpoints

Sensitivity analysis for the key secondary endpoint will include

- a mixed model repeated measure analysis without imputation of missing values (OC-AD).
- a mixed model repeated measure analysis restricted to on treatment values (OC-OT).

The model will include visit-by-treatment interaction and baseline-by-visit interaction. An unstructured covariance structure will be used to model the within-patient errors. Descriptive statistics will be calculated for the value at visit and change from baseline based on OC-AD on the randomised set and based on OC-OT on the treated set.

The primary analysis will be repeated restricted to patients in sensitivity analysis sets SensRS2 and SensRS3.

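### The confirmatory Wilcoxon tests use no baseline covariate; they are valid, but extending the SAP's residual-rank test to KCCQ-TSS and CHQ-SAS dyspnea would be a cheap improvement worth 0 to about 4 power points over assumed correlations

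*SAP*

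**What the plan says.** For the primary endpoint, SAP 7.4.1 says that "change from baseline to week 12 in distance walked in 6 minutes will be evaluated using a normal approximation of the Wilcoxon rank test". It adds: "Any confirmatory conclusion such as for hierarchical testing will be based on the result of the Wilcoxon rank test". For KCCQ-TSS and CHQ-SAS dyspnea, SAP 7.5.1.1 says that each "will be evaluated using a normal approximation of the Wilcoxon rank test using the randomised set". None of the three tests has a covariate, and randomisation is unstratified (Protocol 7.6).

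For these three endpoints, adjustment for baseline appears only in sensitivity analyses:

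- MMRMs with a baseline-by-visit term are planned for all three (SAP 7.4.2 and 7.5.1.2). They use observed data and drop the worst-case ranking.
- For 6MWT alone, SAP 7.4.2 defines a Wilcoxon test on the ranks of residuals from week 12 regressed on baseline, "with patients without week 12 data ranked below any patient with week 12 assessment similar to the rules for primary analysis". It is conditional: "If the mean difference between the treatment groups in 6MWT is above 15m at baseline, the primary analysis will be repeated" with those ranks.

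No residual-rank test is defined for the questionnaires. They are tested confirmatorily only if 6MWT succeeds, and then under Hochberg (SAP 7.5.1). Protocol 7.7.1 describes KCCQ-TSS power as reasonable for a 5-point effect and "a standard deviation that does not exceed 15 points".

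**The concern.** Ranking raw change ignores a baseline value that every change score already needs. If patients who start low tend to gain more, part of the spread in change is predictable from baseline, and removing it sharpens the comparison. The MMRMs cannot recover this, because only the Wilcoxon result counts for confirmation.

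The questionnaires have the most to gain, because their stated power is the lowest in the hierarchy. With 5% missing it is 73% for KCCQ-TSS at SD 15 (61% at alpha 2.5%), 47% at SD 20, and 79% for CHQ-SAS dyspnea at SD 1.4. These are marginal figures. The chance of a confirmatory claim is lower once the 6MWT gate and Hochberg are applied.

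**Working it through.** **Inputs from the documents.** 150 per arm, two-sided alpha 5%, 5% missing per arm ranked worst, normal change scores (Protocol 7.7, 7.7.1). Effects are 30 m with SD 72 m, 5 points with SD 13 to 20, and 0.5 points with SD 1 to 1.4. Reliabilities are 0.88 (KCCQ-TSS) and 0.91 (CHQ-SAS dyspnea), from SAP 9.3.

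**Assumed, not in the documents.** The baseline-change correlation r, the baseline SDs and the correlation between endpoints.

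**Step 1: reproduce the plan.** For 6MWT, p = Phi(-30/(72 x sqrt 2)) = 0.384, and n = (1.960 + 1.282)^2 / (6 x (p - 0.5)^2) = 130.5, so 131 per group as stated. Simulating the normal-approximation Wilcoxon test with 5% ranked worst (40,000 trials per setting) gives:

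- 6MWT: 90.0% (stated 90%)
- KCCQ-TSS at SD 13/15/17/20: 84.9/72.8/61.4/47.2% (stated 85/73/61/47%)
- CHQ-SAS at SD 1/1.2/1.4: 97.6/90.0/78.9% (stated 98/90/79%)

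**Step 2: rerun the same simulated trials with residual ranks.** Regressing week 12 on baseline gives the same residuals as regressing change on baseline. Missing patients stay lowest. Power at alpha 5%, unadjusted to adjusted:

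| Endpoint | r = 0 | r = -0.1 | r = -0.2 | r = -0.3 |
|---|---|---|---|---|
| KCCQ-TSS, SD 15 | 72.8 to 72.6 | 72.8 to 73.1 | 72.8 to 74.5 | 72.9 to 76.9 |
| KCCQ-TSS, SD 20 | 47.2 to 46.9 | 47.2 to 47.3 | 47.3 to 48.6 | 47.2 to 50.8 |
| CHQ-SAS, SD 1.4 | 78.9 to 78.8 | 78.9 to 79.2 | 78.8 to 80.4 | 78.8 to 82.6 |
| CHQ-SAS, SD 1.2 | 90.0 to 89.9 | 90.0 to 90.2 | 90.0 to 91.1 | 90.1 to 92.5 |

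CHQ-SAS at SD 1 gains only 0.5 to 1.0 points at r = -0.2 to -0.3, because power is already near 98%. At alpha 2.5% and r = -0.3 the gain is 4.5 points for KCCQ-TSS (SD 15) and 4.7 for CHQ-SAS (SD 1.4). In sample-size terms, 150/(1 - r^2) - 150 is about 6 patients per arm at r = -0.2 and 15 at r = -0.3.

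**Step 3: which r is plausible?** Suppose true change is unrelated to true baseline. Baseline measurement error alone then gives r = -(1 - reliability) x SD(baseline)/SD(change).

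- KCCQ-TSS, assumed baseline SD 20 to 25, change SD 15: -0.12 x 20/15 = -0.16 to -0.12 x 25/15 = -0.20. Gain 1 to 2 points.
- CHQ-SAS, assumed baseline SD 1.0 to 1.5, change SD 1.4: -0.09 x 1.0/1.4 = -0.06 to -0.09 x 1.5/1.4 = -0.10. Gain under 1 point.

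For KCCQ-TSS a larger r follows if the SD stays about constant. From SD12^2 = SDb^2 + SDc^2 + 2 r SDb SDc with SDc = 15, r = -0.3 needs the SD to grow by 5% (SDb 20) or 0% (SDb 25). r = 0 needs growth of 25% or 17%. This too rests on assumed SDs.

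**Step 4: 6MWT.** Baseline is limited to 100 to 350 m (Protocol 5.1.1). With r = -(1 - slope) x SDb/72, an assumed SDb of 45 to 59 m and a slope of 0.7 to 1, r runs from 0 to -0.3 x 59/72 = -0.25. The gain is 0 to about 2 points.

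**Step 5: gatekept power.** With KCCQ-TSS SD 15, CHQ-SAS SD 1.4 and an assumed between-endpoint correlation of 0 to 0.6, the chance of a confirmatory KCCQ-TSS claim is 64-68% unadjusted. With only the questionnaires adjusted it becomes 65-69% (r = -0.2) or 68-72% (r = -0.3).

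**Step 6: validity.** Under the null the residual-rank test rejects 4.9% of the time with random missing counts. With near-equal missing counts it rejects 3.4%, like the unadjusted test. The gain persists when KCCQ-TSS is bounded at 0 to 100, and when 3% of 6MWT values are 0 m.

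**The case against.** The strongest reply is that nothing is broken. The test is valid, every stated power figure reproduces, and the protocol discloses questionnaire power openly without promising 80% or 90%. All of that stands. A reader might infer that the trial is underpowered against its own claims or that the analysis is wrong; the documents support neither.

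A reader might also take 1 to 4 points as established for both questionnaires. They do not show that. r appears nowhere, and for CHQ-SAS dyspnea the only anchor is the reliability of 0.91, which implies less than 1 point. Protocol 7.7.1 does not even say whether its cited KCCQ-TSS SDs are of the score or of its change.

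Nor is the remedy already written for the questionnaires. SAP 7.4.2 defines it for 6MWT only, so using it elsewhere is an extension that needs its own ordering rule.

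It is also fair that the gain is small beside the declared spread in KCCQ-TSS power (85% down to 47% across SD 13 to 20), and that baseline-adjusted MMRMs are already planned. But the MMRMs drop the worst-case ranking and cannot support a confirmatory claim. The conditional 6MWT test would rarely run: the SE of the baseline difference is 45 to 59 m x sqrt(2/150) = 5.2 to 6.8 m, so a 15 m difference arises by chance in about 0.4 to 3% of trials.

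**Conclusion.** The point holds as a cheap improvement. The three confirmatory tests are sound as written but leave a small amount of power unused if change correlates negatively with baseline.

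Over r = 0 to -0.3 at alpha 5%, the size is 0 to 4 points for KCCQ-TSS, 0 to 4 for CHQ-SAS dyspnea and about 0 to 2 for 6MWT. The figures nearest to the documents are 1 to 2 points for KCCQ-TSS and under 1 for CHQ-SAS dyspnea; both still need an assumed baseline SD. The downside at r = 0 is at most 0.3 points.

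The result rests on assumed r and baseline SDs, a linear relation with baseline and 5% missing per arm. The case is mainly about the questionnaires, and chiefly KCCQ-TSS.

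**What to change.** Before unblinding, amend Protocol 7.1 and 7.3.2 and SAP 7.5.1.1 and 6.6.2. The confirmatory test for KCCQ-TSS and CHQ-SAS dyspnea becomes the Wilcoxon test on residuals of week 12 regressed on baseline. State the ordering explicitly: patients with week 12 data are ranked by residual, and those without are placed below every observed residual in the order of SAP Tables 6.6.2: 1 and 6.6.2: 2. Keep the unadjusted Wilcoxon test and the Hodges-Lehmann estimate as supportive. The same change for 6MWT (Protocol 7.3.1, SAP 7.4.1) is optional, because the gain is small. Running the test unconditionally as a sensitivity analysis would add robustness but recover no confirmatory power.

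The costs are an amendment with ethics and authority approval (Protocol 8.1) and a p-value that no longer corresponds to the Hodges-Lehmann estimate. If 6MWT is left as it is, the hierarchy also loses its single common method. No new data or patients are needed: SAP 6.6.2 already leaves a change score missing when the baseline questionnaire is missing. SAP section 10 records that urine glucose results suggestive of allocation reached sites before database lock. The amendment should therefore be dated and documented as made without unblinded data.

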7.4.2 Sensitivity analysis of the primary endpoint

Sensitivity analysis for the primary endpoint will include;

- a mixed model repeated measure analysis (MMRM) without imputation of missing values (OC-AD).
- an MMRM restricted to on-treatment values (OC-OT).

The model will include visit-by-treatment interaction and baseline-by-visit interaction. An unstructured covariance structure will be used to model the within-patient errors. Descriptive statistics will be calculated for the value at visit and change from baseline based on OC-AD on the randomised set and based on OC-OT on the treated set. The MMRM analyses will also be shown graphically.

The primary analysis will be repeated restricted to patient in the sensitivity analysis set SensRS1, SensRS2 and SensRS3.

If the mean difference between the treatment groups in 6MWT is above 15m at baseline, the primary analysis will be repeated, but using the ranks of the residuals from the following linear regression model

$$6MWT_{12weeks} \sim 6MWT_{Baseline}$$

with patients without week 12 data ranked below any patient with week 12 assessment similar to the rules for primary analysis.

7.4.3 Subgroup analysis of the primary endpoint

The primary analysis of the primary endpoint will be repeated for each subgroup as defined in [Table 6.4: 1](#). A forest plot summarising all subgroup analyses will be shown.

7.5 SECONDARY ENDPOINTS

7.5.1 Key secondary endpoints

If the null hypothesis for the primary analysis of the primary endpoint is rejected, and the result is more favourable for empagliflozin, superiority is concluded in the primary endpoint, and the overall type I error is preserved for the test in the next step. In the next step a Hochberg procedure will be applied to account for multiplicity of testing of the key secondary endpoints:

If the largest p-value of the primary analysis of the two key secondary endpoints is below 5%, both null hypotheses of the key secondary endpoints will be rejected. Otherwise, if the smaller p-value of the primary analysis of the two key secondary endpoints is below 2.5%, only the corresponding null hypothesis can be rejected.

If the primary hypothesis of the primary endpoint is not rejected, the tests of the key secondary endpoints are conducted in an exploratory manner.

7.5.1.1 Primary analysis of the key secondary endpoints

The two key secondary endpoints ‘Change from baseline to week 12 in KCCQ-TSS’ and ‘Change from baseline to week 12 in CHQ-SAS dyspnea score’ are part of the testing strategy.

Both key secondary endpoints ‘Change from baseline to week 12 in heart failure symptoms as measured by the KCCQ TSS’ and ‘Change from baseline to week 12 in CHQ-SAS dyspnea score’ will be evaluated using a normal approximation of the Wilcoxon rank test using the randomised set. For estimation of effect the non-parametric Hodges-Lehmann estimate for the median difference will be calculated.

Change from baseline in both scores will be defined as the endpoint value at week 12 minus the last available endpoint value before start of randomised trial medication.

If no questionnaire is available at week 12, an imputed value as defined in [Section 6.6](#) will be used.

